4.2 Baseline characteristics per randomisation group (collected at Screening)

For all participants that were enrolled, the same baseline characteristics at Screening will be shown in the following table. The differences between all four study arms will be compared by eyeballing; no formal statistical tests will be performed.

The laboratory results of the enrolled and randomized participants (during the Screening visit) will be reported. Some of the tests were only performed in a subset of participants (for instance, participants were ineligible due to being HIV-positive or pregnant, and were therefore not further tested for STIs such as CT, NG, HSV-2, etc). The laboratory results per enrolled arm will also be reported.

Sociodemographics	Group 1 N=17	Group 2 N=17	Group 3 N=17	Group 4 N=17
Kigali neighbourhood (n % per category) ¹				
Age (median, IQR)				
Age, categorised (n % per category)				
- 18 to 25				
- 26 to 35				
- 36 to 45				
Marital status (n % per category)				
Education level (n % per category)				
Sexual history and behaviour	Group 1	Group 2	Group 3	Group 4
Number of sex partners in lifetime (median, IQR)				
Number of sex partners last 12 months (median, IQR)				
Number of sex partners last month (median, IQR)				
Currently has a main sex partner (n %)				
Lives together with main sex partner (n %)				
Main sex partner circumcised (n % per category)				
- Yes				
- Does not know				
- No				
Main sex partner has other sex partners (n % per category)				
- Yes				
- Does not know				
- No				
Vaginal sex frequency last 2 weeks (median, IQR)				
Any condom use in past two weeks (n %)				
Condom use during last sex act (n %)				
Exchanged sex for money/goods in past month (n %)				
Reproductive and contraceptive history	Group 1	Group 2	Group 3	Group 4
Pregnancies in lifetime (median, IQR)				
Deliveries in lifetime (median, IQR)				
Miscarriages in lifetime (median, IQR)				
Varcian 9 November 2016				11

Currently breastfeeding (n %)				
Ever severe infection with fever during pregnancy/childbirth				
(n %)				
Ever baby with severe infection with fever within days after				
birth (n %)				
Currently using a modern method of contraception other				
than condoms (n % per category): - Pills				
- Injections				
- Implant				
- Copper IUD - Sterilised				
- Other (described in footnote)	Crear 1	C	C	Current A
Medical history	Group 1 N=17	Group 2 N=17	Group 3 N=17	Group 4 N=17
Any significant medical and/or surgical history or current				
condition (n %; describe in footnote)				
Ever had surgery (n %; describe in footnote)				
Any chronic diseases (n %; describe in footnote)				
Ever treated for BV (n %)				
Ever treated for vaginal candidiasis (n %)				
Treated for STI in the past 12 months (n %)				
Current medications and symptoms	Group 1	Group 2	Group 3	Group 4
Any current medication use (n %; describe in footnote)				
Any urogenital symptoms now or in last 2 weeks, patient-				
reported (n%)				
If yes, what symptoms ² (n % per category):				
– Burning when passing urine				
– Frequent urination or urgent need to urinate				
-Blood in urine				
-Genital burning				
-Genital itching				
– Pain during sex				
–Lower abdominal pain				
– Unusual vaginal discharge				
-Sores in the genital and/or anal area (including buttocks)				
 Other (additional categories to be added if needed) 				
If yes, already received treatment (n %)				
If yes, some or all of the symptoms currently ongoing (n %)				
Medical procedures by study physician	Group 1	Group 2	Group 3	Group 4
Any abnormal pelvic exam findings (n % per category)				
Any abnormal bimanual exam findings (n % per category)				
Clinical diagnosis (n % per category)				
Treatment given (n % per category)				
Laboratory results	Group 1	Group 2	Group 3	Group 4
Nugent 4-10 on Gram stain (n %)		•		
Nugent 7-10 on Gram stain (n %)				
Nugent 4-6 on Gram stain (n %)				
TV by InPouch culture (n %)		 		
Version 8 November 2016			1	L

Candida on wet mount (n %)		
HSV-2 serology positive ³ (n %)		
CT PCR positive (n %)		
NG PCR positive (n %)		
Positive for either CT or NG by PCR (n %)		

1. If missing values, a footnote detailing the number of missing values for a particular variable will be added to the table.

2. Percentages can add to more than 100% because participants were allowed to give multiple answers.

3. Kalon HSV-2 test (Kalon, Guildford, United Kingdom), with optical density (OD) > 1.1 of the mean OD of the cut-off defined as positive) and < 0.9 of the OD of the cut-off defined as negative.

4.3 Other baseline characteristics by randomisation group (collected at Enrolment)

Vaginal practices	Group 1 N=17	Group 2 N=17	Group 3 N=17	Group 4 N=17	Total N=68
Weekly frequency of washing body (median, IQR)					
Ever washing the genitalia, and if yes, location of					
washing (n % per category) ¹					
- Yes, outside only					
- Yes, both inside and outside					
- Yes, inside only					
- No					
Weekly frequency of cleaning inside the vagina					
(median, IQR)					
Timing of cleaning inside the vagina (n % per category) ²					
- Before sex					
- After sex					
- While bathing					
- During/after menses					
- Other (described in a footnote)					
Vaginal practices in the past 12 months, other than					
vaginal practices to manage menses (n % per category) ²					
- Water only using fingers					
 Water and soap using fingers 					
 Water with paper/cloth/cotton wool 					
 Water and soap with paper/cloth/cotton wool 					
 Paper, cloth, cotton, wool without liquid 					
- Traditional herbs, stones, or powder					
- Western vaginal medicine					
 Other (described in a footnote) 					
- No vaginal practices					
Practices to manage menstrual blood or spotting in the					
past 12 months (n % per category) ²					
- Tissue, toilet paper, paper, cloth or cotton wool put					
inside the vagina					
- Tissue, toilet paper, paper, cloth or cotton wool					
placed in underwear					
- Sanitary pad					
- Tampon					
 Water, without soap, inside the vagina 					
 Water, with soap, inside the vagina 					

- Other (describe in a footnote)					
- Nothing was used					
- Did not have menses in past 12 months					
Used anything inside the vagina other than plain water					
in the last two weeks (n/N %)					
If yes, what was used (n/N % per category) ¹					
- Soap					
- Soap - Paper/cloth/cotton wool					
- Tampon					
- Traditional herbs, stones or powders					
- Western vaginal medicine					
- Other (described in a footnote)					
	Group 1	Group 2	Group 3	Group 4	Total
Menses	N=17	N=17	N=17	N=17	N=68
Regular menstrual cycle (n % per category)					
- Yes					
- No, irregular					
- Amenorrhea due to hormonal contraception					
- Amenorrhea due to other reason (described in a					
footnote)					
Duration of bleeding(median, IQR)					
Amount of bleeding (n % per category)					
- Light					
- Moderate					
- Heavy					
History of painful periods (n %)					
Self-reported vaginal sex during menses in the past 12					
months (n %)					
Probiotics	Group 1	Group 2	Group 3	Group 4	Total
Ever heard of 'probiotics' before this study (n %)					
Ever bought probiotic pills for oral use in a store or on a					
market (n %)					
If yes, used any probiotic pills in past two weeks (n %)					
Frequency of eating yoghurt (n %)					
Frequency of eating yoghurt (n %) - Never					

1. If missing values, a footnote detailing the number of missing values for a particular variable will be added to the table.

2. Percentages can add to more than 100% because participants were allowed to give multiple answers.

5. Associations between laboratory results and signs/symptoms

All women at all study visits were tested for BV by Amsel criteria, BV by Nugent scoring, TV by wet mount, TV by InPouch culture and vaginal candidiasis by wet mount. For the analyses described in this section, all laboratory results at all study visits will be used.

Modified Amsel criteria (n %)	Nu	igent score	Total	Fisher's	
	0-3	4-6	7-10	TOLAI	exact p ¹
Positive					
Negative]
Total					
Vaginal pH (n %)					
≥ 4.5					
< 4.5					
Total]
>20% Clue cells on wet mount (n %)					
Positive					
Negative					
Total					
KOH/amine test (n %)					
Positive					
Negative					
Total					
Candida on wet mount (n %)					
Positive					
Negative					
Total					
TV on wet mount (n %)					
Positive					
Negative					
Total					
TV InPouch culture (n %)					
Positive					
Negative					
Total					
Unusual vaginal discharge					
self-reported (n%)					
Present					
Absent					
Total					
Unusual vaginal discharge					
clinician observed (n %)					1
Present					1
Absent					4
Total					
Abnormal genital odour					
clinician observed (n %)					
Present					
Absent					
Total					

1. When p<0.05, Nugent 4-6 and Nugent 7-10 will each be compared to Nugent 0-3.

The sensitivity, specificity, positive predictive value and negative predictive value of the modified Amsel criteria compared to the Nugent score (with 7-10 defined as positive, 0-3 as negative) will also be calculated.

	TV c	ulture		OR	Fisher's	
TV on wet mount (n %)	Positive (n%)	Negative (n%)	Total	(95% CI) ¹	exact p	
Positive						
Negative						
Total						
Unusual vaginal discharge self-reported (n %)						
Present						
Absent						
Total						
Unusual vaginal discharge clinician observed (n %)						
Present						
Absent						
Total						
Vaginal itching self-reported (n %)						
Present						
Absent						
Total						

The sensitivity, specificity, positive predictive value and negative predictive value of TV on wet mount compared to TV culture will also be calculated.

Unusual vasinal discharge	Candida or	n wet mount		OR	Fisher's
Unusual vaginal discharge self-reported (n %)	Positive (n %)	Negative (n %)	Total	(95% CI) ¹	exact p
Present					
Absent					
Total					
Unusual vaginal discharge					
clinician observed (n %)					
Present					
Absent					
Total					
Vaginal itching self-reported (n %)					
Present					
Absent					
Total					

6. Analyses of follow-up data: primary efficacy outcomes

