3.1 Retention (see also the flow diagram in Figure 1 above)

	N
Number of women who attended a Screening visit	176
Number of women who attended an Enrolment visit	74
Number of women who were randomised	68
Number of women who attended D7, M1, M2, and M6 visits	66, 67, 66, 64
Number of women who completed all scheduled study visits	60
Number of women who missed visits after randomisation	8
Number of women who withdrew early	4
Number of women who were lost-to-follow-up	0
Number of deaths	0
Number of completed study visits by randomised women, including the Enrolment visit	324
Number of skipped visits after randomisation	4
Number of missed visits after randomisation	12
Total person-months of data collected after randomisation	TBD
Total person-days of data collected after randomisation	TBD

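### SAP section 5 pools repeat visits by the same women into Fisher's exact tests and odds-ratio intervals with no stated allowance for clustering; the p-values, and the TV and Candida intervals, will be too optimistic if both variables persist within a woman

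*SAP*

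**What the plan says.** SAP section 5 (Associations between laboratory results and signs/symptoms) sets the unit of analysis: "For the analyses described in this section, all laboratory results at all study visits will be used". It then lays out three sets of tables:

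- **By Nugent category** (0-3, 4-6, 7-10): modified Amsel, its components, Candida, TV, discharge and odour. There is one inferential column, Fisher's exact p. A footnote adds a gate: "When p<0.05, Nugent 4-6 and Nugent 7-10 will each be compared to Nugent 0-3".
- **By TV culture**: TV on wet mount, discharge and itching, with odds ratio, 95% interval and Fisher's exact p.
- **By Candida on wet mount**: discharge and itching, with the same columns.

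Accuracy measures are added for modified Amsel against Nugent and for TV: "The sensitivity, specificity, positive predictive value and negative predictive value of TV on wet mount compared to TV culture will also be calculated". No interval is planned for them.

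Section 5 does not mention repeated visits, robust variance or a one-visit-per-woman rule. The odds-ratio columns carry a footnote mark whose text does not appear in the document as supplied. Elsewhere the SAP does plan a repeated-measures model: section 6.4 uses GEE for the Nugent efficacy outcomes.

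**The concern.** Fisher's exact test and a standard 2x2 odds-ratio interval treat each row as an independent observation. Here a randomised woman can contribute Screening, Enrolment, D7, M1, M2 and M6. If her laboratory state and her sign or symptom both tend to recur, her visits carry less information than the same number of visits from different women.

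Such persistence is plausible. Protocol 3.1 puts BV recurrence at around 50% within 6 months, and SAP 6.1 says BV and candidiasis were treated in follow-up only when symptomatic, so untreated states can carry over between visits.

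What is at stake is which signs and tests are reported as tracking BV, TV or Candida. Weak associations could pass p<0.05 too easily, and the gate would pass that on to the follow-on comparisons of Nugent 4-6 and 7-10 with 0-3.

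**Working it through.** **1. Share of visits from the same women (SAP 3.1).** Inputs: "Number of women who attended a Screening visit 176"; "Number of women who attended an Enrolment visit 74"; "Number of women who were randomised 68"; attendance at D7, M1, M2 and M6 of 66, 67, 66 and 64; 324 completed visits by randomised women from Enrolment onward.

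- From attendance: all visits 176 + 74 + 66 + 67 + 66 + 64 = 513. From randomised women: 68 (Screening) + 68 (Enrolment) + 66 + 67 + 66 + 64 = 399. Share 399/513 = 77.8%.
- From the stated 324: (324 + 68)/(176 + 324 + 6) = 392/506 = 77.5%, where 6 = 74 - 68 non-randomised women at Enrolment.
- The 324 equals 68 x 5 - 12 missed - 4 skipped, whereas attendance sums to 331. Using 324, 328 or 331, with 176 or 174 screened (section 4.1 says 174) and with or without the 6, the share stays between 77.5% and 79.0%.
- For laboratory results this is roughly a lower bound. SAP 4.1 says HIV-positive or pregnant women were not always examined or tested further. If 30 or 60 of the screened women had no result, the share would be 392/476 = 82% or 392/446 = 88%.

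**2. Design effect for an association.** Assumed cluster sizes consistent with the stated counts: 60 women x 6 visits, 8 x 4, 6 x 2, 102 x 1, giving 506 visits from 176 women.

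Weighted mean cluster size m_w = sum(m²)/sum(m) = (2160 + 128 + 24 + 102)/506 = 2414/506 = 4.77.

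Design effect DE = 1 + (m_w - 1) x ICC_x x ICC_y. The documents give no intraclass correlation (ICC), so these values are assumptions:

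| ICC of each variable | DE | Effective N | True SE / naive SE | Approx. type I error |
|---|---|---|---|---|
| 0 for either | 1.00 | 506 | 1.00 | 5% |
| 0.1, 0.1 | 1.04 | 488 | 1.02 | 5.4% |
| 0.2, 0.2 | 1.15 | 440 | 1.07 | 6.8% |
| 0.3, 0.3 | 1.34 | 378 | 1.16 | 9.0% |
| 0.5, 0.5 | 1.94 | 260 | 1.39 | 16.0% |

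Beta-binomial simulation with no true association (3,000 replicates per setting) agrees. Fisher type I error is about 6%, 8-9% and 14-15% at ICC 0.2, 0.3 and 0.5. Coverage of the nominal 95% odds-ratio interval is about 93%, 90-91% and 84-85%.

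**3. Does the correlation pattern matter?** Latent-normal binary data, no true association, 3,000 to 4,000 replicates per setting, prevalences 0.35/0.30 and 0.10/0.30, same latent correlation in both variables. The ranges cover repeated runs with slightly different cluster sizes:

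| Latent correlation | Constant over all visits | Decaying by visit (adjacent-visit value shown) |
|---|---|---|
| 0.3 | 4-6% | 4-5% |
| 0.5 | 7-10% | 5-6% |
| 0.7 | 12-15% | 8-10% |

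The two scales fit together: at prevalence 0.30-0.35, latent 0.3, 0.5 and 0.7 correspond to binary ICCs of about 0.18, 0.32 and 0.48.

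**The case against.** The strongest reply is that the harm is conditional and the analysis minor. Most of that stands.

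- **Both variables must be correlated within woman.** If either is not, there is no inflation. The trial also disrupts persistence: BV/TV was treated before Enrolment, randomisation required no BV by Amsel and no TV on wet mount, and TV was always treated in follow-up. Decaying correlation is therefore credible, and it roughly halves the excess error or better at latent 0.5 and 0.7.
- **Many rows have no live null hypothesis.** Clue cells, pH, amine test and modified Amsel against Nugent measure the same condition; TV wet mount and culture detect the same organism. Those associations will appear whatever the variance method.
- **Section 5 serves no objective or endpoint listed in SAP section 2**, and the study is a pilot without formal sample size calculations.
- **The missing footnote text** means a stated odds-ratio method cannot be ruled out. The Fisher p-values do not depend on it.

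A reader might infer that intervals are too narrow throughout section 5. The documents do not support that: the Nugent tables have p-values only, and sensitivity, specificity and predictive values have no planned interval. A reader might also infer that the p-values are certainly too small, or that the efficacy or safety findings are affected. The first needs a correlation the documents do not give; the second fails because no such comparison uses section 5.

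None of this removes the core point: the plan names a test for independent observations and applies it to repeated ones.

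**Conclusion.** The concern holds in a limited, conditional form. Pooling visits into Fisher's exact tests, and into odds-ratio intervals for TV culture and Candida, is the stated method, and about 78% of attended visits come from 68 women.

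If both variables are positively correlated within woman, the p-values and those intervals will be too optimistic. The size cannot be computed from the documents. Under the assumed latent correlations it ranges from negligible (about 4-6% type I error at 0.3) to material (about 8-15% at 0.7), with the lower figures applying if correlation fades across visits.

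The exposure lies mainly in the symptom and sign rows and in the Candida and TV rows against Nugent score. It is worth correcting because the remedy is already in the SAP's toolkit, not because any main conclusion rests on it.

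**What to change.** In SAP section 5:

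1. Keep the all-visit counts, and the point estimates of sensitivity, specificity and predictive values, as visit-level description.
2. Take the p-values, including the one that triggers the follow-on Nugent comparisons, and the odds-ratio intervals from logistic GEE with robust variance clustered on the woman. Where cells are sparse and GEE may not converge, as could happen for TV wet mount against culture, use a bootstrap or permutation that resamples whole women.
3. If intervals are added for the accuracy measures, cluster them in the same way.
4. Optionally add Fisher tests on the Screening visit alone as a sensitivity analysis. They should not replace the main analysis: they keep 176 of about 513 visits (34%) and drop about two thirds.
5. State the odds-ratio interval method in the section.

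The cost is revised wording, a little more analysis and possibly somewhat wider intervals. No new data are needed. If within-woman correlation proves small, the results will barely change.

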BV is a complex condition involving multiple bacteria and can therefore be defined in multiple ways. In clinic settings, it is often diagnosed based on patient-reported symptoms alone or using the Amsel criteria (5). In the case of Amsel criteria, BV is diagnosed when 3 of the following 4 criteria are present: 1) clue cells on wet mount microscopy (a wet mount is vaginal fluid on a microscopy slide); 2) a 'fishy' odour after adding 10% KOH to the wet mount; 3) vaginal pH > 4.5; and 4) thin, homogenous vaginal discharge present. Both patient-reported symptoms as well as the Amsel criteria have poor sensitivity because many women with BV are asymptomatic. Therefore, in research settings, Gram stain Nugent scoring is more often used (6). Vaginal fluid is smeared on a microscopy slide, stained, and scored under the microscope based on the presence and relative quantity of three bacterial morphotypes (shapes). In this case, the diagnosis does not depend on the presence of signs or symptoms and is therefore more sensitive. A Nugent score of 0-3 is considered normal, 4-6 is referred to as intermediate microbiota, and 7-10 BV. Unfortunately, Nugent scoring is labour-intensive and is therefore usually not a feasible alternative to the Amsel criteria. Other microorganisms that are often found in the vagina include Candida yeasts, Trichomonas vaginalis (TV) and other sexually transmitted pathogens. Vaginal candidiasis and TV are typically diagnosed by visualising the organisms on the wet mount by microscopy and/or by culturing them, and other sexually transmitted pathogens by commercialised pathogen-specific diagnostic assays.

Epidemiological studies using the Amsel criteria or Nugent scoring have shown that BV increases risk of preterm birth and infections in pregnant women and their neonates (7). Furthermore, BV and intermediate microbiota by Nugent score, TV and vaginal candidiasis, have been associated with increased transmission of HIV and other chronic sexually transmitted infections (STIs) (8). Studies have also shown that the female urinary tract has its own microbiome that resembles the VMB, and presence of *E. coli* in the VMB might therefore increase risk of urinary tract infections (UTIs) (9).

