1.2 Visit windows and retention definitions

Visit windows for the study visits were as follows:

- Screening + results visits: the entire screening process should not have taken longer than 6 weeks
- Enrolment visit: maximum of 3 days after completion of oral metronidazole treatment
- Day 7: Day 5 Day 9
- Month 1: ± 7 days
- Month 2: ± 7 days
- Month 6: ± 7 days

The following retention definitions were used:

- Early withdrawal: The participant informed a RU staff member that she no longer wants to participate in the study.
- Late visit: The participant did attend a study visit but after the visit window had closed.
- Skipped visit: The participant did not attend a study visit but did return to the study clinic for a subsequent study visit.
- Lost-to-follow-up: RU does not label a participant as lost to follow-up until study close-out. A participant is considered lost to follow-up at study close-out when multiple contact attempts by RU staff failed (as specified in the RU SOP for Retention) and the participant did also not return to the study clinic spontaneously before study close-out.
- Missed visit: All visits that should have taken place according to the study protocol but did not. This includes all study visits after an early withdrawal or after the last study visit made by a participant who is lost to follow-up, as well as all skipped visits.

2. Primary and secondary clinical endpoints

The endpoints of the study discussed in this SAP are:

Primary clinical objectives	Endpoints
1. To determine the safety of the	- Self-reported solicited and unsolicited (serious) adverse events
three biomedical interventions	(AEs) and social harms
compared to the control group.	 Clinician-observed speculum exam findings
2. To determine the preliminary	– BV by Amsel criteria, Nugent score 4-10* (versus 0-3), TV by
efficacy of the three biomedical	culture and symptomatic vaginal candidiasis at any time during
interventions compared to the	the intervention (Day 7, Month 1, Month 2)
control group in reducing BV	– BV by Amsel criteria, Nugent score 4-10* (versus 0-3), TV by
recurrence without increasing	culture, and symptomatic vaginal candidiasis after cessation of
vaginal candidiasis incidence.	the intervention (Month 6)
	* Abnormal Nugent scores will also be analysed as Nugent score
	7-10 versus 0-6.
Secondary clinical objectives	Endpoints

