6.1 Intent-to-treat incidence rates of primary efficacy outcomes

All women at all study visits were tested for BV by Amsel criteria, BV by Nugent scoring, TV by wet mount, TV by InPouch culture and vaginal candidiasis by wet mount.

During follow-up, antibiotic and antifungal treatments were given as follows:

- BV was only treated when a woman had BV by Nugent score or modified Amsel criteria but also reported symptoms typical for BV (unusual vaginal discharge, fishy smell) or these were observed by the study physician during a pelvic examination. A diagnosis could almost always be made on the day of the study visit.
- TV was always treated when identified on wet mount or by TV culture. The wet mount results were always available on the day of the study visit, but the InPouch culture results only 5 days later. If a woman had tested negative by wet mount but positive by InPouch culture, she was asked to return to the RU clinic for treatment.
- Vaginal candidiasis was only treated when Candida was present on the wet mount and the participant reported symptoms that are typical for vaginal candidiasis (itching, curd-like discharge) or these were observed by the study physician during a pelvic examination. A diagnosis could almost always be made on the day of the study visit.

We will describe any antibiotic or antifungal use between randomisation and M2 and between M2 and M6 by indication, drug type and drug dosing schedule.

Each positive case during follow-up will be assessed separately to differentiate between incident infections and persistent infections. We will assess whether treatments were dispensed appropriately and whether participants adhered to the treatments.

The incidence of each primary outcome will be defined as follows:

- Incident BV by modified Amsel criteria: positive by modified Amsel criteria after having been negative by modified Amsel criteria at the previous visit or after a case of symptomatic BV (diagnosed by modified Amsel criteria or by Nugent score) was adequately treated.
- Incident BV by Nugent score 4-10: a Nugent score of 4-10 after a Nugent score of 0-3 at the previous visit or after a case of symptomatic BV (diagnosed by modified Amsel criteria or by Nugent score) was adequately treated.
- Incident BV by Nugent score 7-10: a Nugent score of 7-10 after a Nugent score of 0-6 at the previous visit or after a case of symptomatic BV (diagnosed by modified Amsel criteria or by Nugent score) was adequately treated.

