6.4 Adjustment for confounding: generalised estimating equation (GEE) models

Other behavioural and clinical characteristics might also influence the primary efficacy outcomes. Some of these variables were collected at baseline but also at the M2 and M6 visits.

Sexual behaviour	Baseline	M2	M6	p-value ²
Number of sex partners in last month at baseline or per				
month during follow-up period (median, IQR)				
Currently has a main sex partner (n %) ¹				
Obtained a new main partner during period (n %)	NA			
Lives together with main sex partner (n %)				
Main sex partner circumcised (n % per category)				
- Yes				
- Does not know				
- No				

We will assess any behavioural changes over time in the total study population as follows:

Main sex partner has other sex partners (n % per category)				
- Yes				
- Does not know				
- No				
Vaginal sex frequency last 2 weeks (median, IQR)				
Any condom use in past two weeks (n %)				
Exchanged sex for money/goods in past month (n %)				
Contraceptive practices, vaginal practices, menses	Baseline	M2	M6	p-value ²
Currently using a modern method of contraception other				
than condoms (n % per category):				
- Pills				
- Injections				
- Implant				
- Copper IUD				
- Sterilised				
- Other				
Weekly frequency of vaginal practices since the last visit				
(includes water only using fingers, water and soap using				
fingers, paper/cloth/cotton wool with or without liquid, and				
traditional herbs, stones, or powders)				
Amenorrhea due to hormonal contraception (n %)				
Amenorrhea due to other reason (n %)				
If no amenorrhea, duration of bleeding (median, IQR)				
If no amenorrhea, any vaginal sex during menses (n %)				

1. If missing values, a footnote detailing the number of missing values for a particular variable will be added to the table.

2. McNemar's test for binary or categorical variables and Wilcoxon test for medians.

We will use generalised estimating equation (GEE) models with Nugent 4-10 (compared to Nugent 0-3) at any study visit after randomisation as the outcome and randomisation group as the main predictor (and indicator variable with Group 1 as the reference group) to adjust for the potential effects of these characteristics. A similar model will be run with Nugent 7-10 (compared to Nugent 0-6) as the outcome.

Assessment for effect modification:

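### The accuracy of the modified Amsel criteria is computed without the Nugent 4-6 visits, on a contrast that matches neither planned Nugent endpoint coding

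*SAP*

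**What the plan says.** SAP section 5 cross-tabulates the modified Amsel result against Nugent score in three columns (0-3, 4-6, 7-10). It opens by fixing the data set: "For the analyses described in this section, all laboratory results at all study visits will be used". A footnote deals with the intermediate column in the significance tests: "When p<0.05, Nugent 4-6 and Nugent 7-10 will each be compared to Nugent 0-3". The accuracy measures are then defined "with 7-10 defined as positive, 0-3 as negative". Nothing is said about where 4-6 goes.

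Elsewhere the SAP uses two Nugent dichotomies.

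- **4-10 versus 0-3.** This is listed first in the endpoint table (SAP section 2). In section 6.1 an incident case is "a Nugent score of 4-10 after a Nugent score of 0-3 at the previous visit".
- **7-10 versus 0-6.** The note to the endpoint table introduces it ("Abnormal Nugent scores will also be analysed as Nugent score" 7-10 versus 0-6). In section 6.1 an incident case is "a Nugent score of 7-10 after a Nugent score of 0-6 at the previous visit", and for the GEE models in section 6.4, "A similar model will be run with Nugent 7-10 (compared to Nugent 0-6) as the outcome".

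Protocol section 3.1 gives the meaning of the categories: "A Nugent score of 0-3 is considered normal, 4-6 is referred to as intermediate microbiota, and 7-10 BV".

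**The concern.** A clinician holding an Amsel result does not know which women are intermediate. SAP section 6.3 says that Nugent scores arrived after enrolment decisions had been made. Predictive values computed after removing the 4-6 visits therefore do not apply to the set of women actually tested.

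The chosen contrast also takes its sensitivity from one endpoint coding (7-10 versus 0-6) and its specificity from the other (4-10 versus 0-3). If Amsel positivity rises across the three Nugent categories, each of these is the more favourable of the two available values, and neither planned endpoint has that pair.

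This matters because modified Amsel is itself a primary outcome and a negative result was required for randomisation. SAP section 6.3 reports that some women randomised on that basis turned out to have Nugent 7-10. A reader will look to section 5 to judge how far the two measures agree.

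**Working it through.** The documents state no accuracy figure and no cell counts, so there is nothing to reproduce. The directions follow from algebra; the sizes rest on assumed rates.

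**Notation.** Let a, b, c be the shares of visits at Nugent 0-3, 4-6 and 7-10, and fa, fb, fc the proportions Amsel-positive in each.

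| Measure | SAP rule (7-10 v 0-3) | 7-10 v 0-6 | 4-10 v 0-3 |
|---|---|---|---|
| Sensitivity | fc | fc | (b·fb + c·fc)/(b + c) |
| Specificity | 1 − fa | 1 − (a·fa + b·fb)/(a + b) | 1 − fa |
| PPV | c·fc/(c·fc + a·fa) | c·fc/(c·fc + a·fa + b·fb) | (b·fb + c·fc)/(a·fa + b·fb + c·fc) |
| NPV | a(1−fa)/[a(1−fa) + c(1−fc)] | [a(1−fa) + b(1−fb)]/[a(1−fa) + b(1−fb) + c(1−fc)] | a(1−fa)/[a(1−fa) + b(1−fb) + c(1−fc)] |

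**Directions.** Against 7-10 v 0-6, the SAP rule:
- overstates PPV as soon as one 4-6 visit is Amsel-positive;
- overstates specificity only if fb > fa;
- leaves sensitivity unchanged;
- if anything understates NPV.

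Against 4-10 v 0-3, it:
- leaves specificity unchanged;
- overstates sensitivity if fb < fc;
- overstates NPV as soon as one 4-6 visit is Amsel-negative;
- if anything understates PPV.

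**Illustration (all rates assumed).** Take a, b, c = 0.55, 0.20, 0.25 and fa, fb, fc = 0.05, 0.40, 0.75.

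Amsel-positive shares: 0.55 × 0.05 = 0.0275; 0.20 × 0.40 = 0.08; 0.25 × 0.75 = 0.1875. Amsel-negative shares: 0.5225; 0.12; 0.0625.

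| Measure | SAP rule | 7-10 v 0-6 | 4-10 v 0-3 |
|---|---|---|---|
| Sensitivity | 0.1875/0.25 = 75% | 0.1875/0.25 = 75% | 0.2675/0.45 = 59% |
| Specificity | 0.5225/0.55 = 95% | 0.6425/0.75 = 86% | 0.5225/0.55 = 95% |
| PPV | 0.1875/0.215 = 87% | 0.1875/0.295 = 64% | 0.2675/0.295 = 91% |
| NPV | 0.5225/0.585 = 89% | 0.6425/0.705 = 91% | 0.5225/0.705 = 74% |

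**Range.** Keep c = 0.25, fa = 0.05 and fc = 0.75, and let b run over 0.10-0.30 and fb over 0.20-0.60.

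- 7-10 v 0-6 specificity runs from (0.4275 + 0.12)/0.75 = 73% to (0.6175 + 0.08)/0.75 = 93%, against 95% under the SAP rule.
- 7-10 v 0-6 PPV runs from 0.1875/(0.1875 + 0.0225 + 0.18) = 48% to 0.1875/(0.1875 + 0.0325 + 0.02) = 78%. At the same two corners the SAP rule gives 0.1875/0.21 = 89% and 0.1875/0.22 = 85%.
- 4-10 v 0-3 sensitivity runs from (0.06 + 0.1875)/0.55 = 45% to (0.06 + 0.1875)/0.35 = 71%, against 75% under the SAP rule.

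**A milder case.** Protocol section 5.1 gives a BV prevalence of 40%. With shares 50/10/40% and positivity 5/40/80%, the SAP rule gives specificity 95.0%, PPV 92.8% and NPV 85.6%. Coding 7-10 v 0-6 gives 89.2%, 83.1% and 87.0%.

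**Boundary.** With the same shares and fb = fa = 5%, specificity does not move (95.0%) and PPV falls only to 91.4%. With fb = 2%, below fa, specificity rises to 95.5%.

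**The case against.** The strongest defence is that the choice is reasonable and open to inspection. Nugent 4-6 is by definition neither normal nor BV, section 5 uses 0-3 as its reference in the pairwise tests too, and comparing clear BV with clear normal is a recognisable contrast. The planned three-column table would let a reader recompute everything. This stands as a limit on severity. It does not justify headline measures that omit a class without saying so, beside a statement that all results are used.

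A reader might infer several stronger things that the documents do not support.

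- **That accuracy is inflated throughout.** It is not. Against 7-10 v 0-6, sensitivity is unchanged and NPV is slightly understated. Against 4-10 v 0-3, PPV is understated. The enrolment error described in SAP section 6.3 (Amsel-negative, Nugent 7-10) concerns sensitivity and NPV, and under 7-10 v 0-6 neither gets worse.
- **That 7-10 v 0-6 is the trial's one Nugent endpoint.** The coding listed first is 4-10 v 0-3, so correcting towards 7-10 v 0-6 alone would leave that endpoint uncovered.
- **That modified Amsel decided who was treated at screening.** The SAP, describing what was done, reports treatment at screening on Nugent score and/or TV (section 1.1 and Table 1, footnote 3). During follow-up, section 6.1 accepts Nugent or modified Amsel together with symptoms or signs.
- **That these figures will set the criterion for the efficacy trial.** The pilot is meant to inform that trial, but no passage gives this role to the section 5 measures. The early Amsel-Nugent comparison in Protocol section 6.4 served a decision within this study.

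It is also fair to say that section 5 pools repeated visits, before and after treatment. Predictive values will describe that mixture under any coding, and the fix below does not change that.

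**Conclusion.** The point holds as a minor one. The accuracy rule drops the 4-6 visits without saying so, conflicts with the section's own statement on data use, and matches neither planned Nugent coding. That much follows from the text alone.

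The size is unknown. In the illustration the largest gaps are 23 points of PPV (87% v 64%) and 9 of specificity (95% v 86%) against one coding, and 16 points of sensitivity (75% v 59%) and 15 of NPV (89% v 74%) against the other. These depend on how many visits score 4-6 and how often they are Amsel-positive, and the documents give neither. The specificity gap requires 4-6 visits to be Amsel-positive more often than 0-3 visits. That is plausible for an intermediate category but is not documented. No efficacy estimate is affected.

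**What to change.** In SAP section 5, define the four measures twice, using every visit that has both results: once with Nugent 7-10 positive and 0-6 negative, and once with 4-10 positive and 0-3 negative. Keep 7-10 versus 0-3 as a secondary figure, labelled as excluding intermediate visits, with the number excluded.

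The cost is one extra calculation from cells already in the planned three-column table; no new data are needed. Some figures will look less favourable (specificity and PPV under the first coding, sensitivity and NPV under the second, on the assumptions above), and others will be the same or slightly better.
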